### **10.2. Subject withdrawal (Amended: 14 May 2018)**

Subjects who are withdrawn because of SAEs/AEs must be clearly distinguished from subjects who are withdrawn for other reasons. Physicians will follow subjects who are withdrawn as result of a SAE/AE until resolution of the event (see Section 8.5).

Withdrawals will not be replaced.

**CONFIDENTIAL**208710 (EPI-HPV-077 VS KR PMS)  
Protocol Amendment 1 Final**10.2.1. Subject withdrawal from PMS**

From an analysis perspective, a ‘withdrawal’ from the PMS refers to any subject who did not come back for the concluding visit/was not available for the concluding contact foreseen in the protocol.

All data collected until the date of withdrawal/last contact of the subject will be used for the analysis.

A subject is considered a ‘withdrawal’ from the PMS when no PMS procedure has occurred, no follow-up has been performed and no further information has been collected for this subject from the date of withdrawal/last contact.

Physicians will make **attempts** to contact those subjects who do not return for scheduled visits or follow-up.

Information relative to the withdrawal will be documented in the CRF. The physician will document whether the decision to withdraw a subject from the PMS was made by the subject’s parent(s) or LAR(s), or by the physician, as well as which of the following possible reasons was responsible for withdrawal:

- Serious adverse event.
- Non-serious adverse event.
- Protocol violation (specify).
- Consent withdrawal, not due to an adverse event.
- Lost to follow-up.
- Death.
- Other (specify).

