#### **11.5.2. Analysis of safety**

Safety analysis based on total vaccinated cohort, will include all subjects who were vaccinated per product information and have completed 30-day follow-up after at least one dose, regardless of the number of dose. Analysis of AE/SAE data reported after each dose will be performed separately.

**CONFIDENTIAL**208710 (EPI-HPV-077 VS KR PMS)  
Protocol Amendment 1 Final**11.5.2.1. Within group assessment**

The AEs/ SAEs will be analysed in the PMS report according to the expectedness and unexpectedness criteria. (Refer to **GLOSSARY OF TERMS** for the definitions of expected AEs and unexpected AEs).

The number and percentage, with exact 95% confidence interval (CI), of any AEs occurring within 30 days (**Day 1 to Day 30**) will be tabulated, for each dose, for overall doses and by number of subjects. The same calculations will be done for any adverse events according to the severity and for those assessed as causally related to vaccination.

The verbatim reports of signs and symptoms will be matched and coded according to the appropriate WHO-ART Preferred Term. The PMS physician will review and confirm the appropriate WHO-ART Preferred Term by responding to data queries if any discrepancies are reported while coding. The percentage of subjects with AEs occurring within 30 days (**Day 1 to Day 30**) with its exact 95% CI will be tabulated by preferred term. Similar tabulation will be done for AEs with relationship to vaccination and for AEs rated as grade 3.

The number and percentage of subjects who received concomitant medication/ vaccination at least once during the 30-day (**Day 1 to Day 30**) follow-up period will be tabulated after each vaccine dose and overall, with exact 95% CI. Similar tabulations will be done for the number of subjects by types of medication/ vaccination during the entire PMS period.

The outcome of pregnancy (reported in the pregnancy report form) for subjects who become pregnant subjects during PMS will be presented, If possible.

Serious adverse events and withdrawals due to adverse events reported during the PMS period (each subject receiving the vaccine up to 30 days after the last dose) will be described in detail.

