6.8 Safety Evaluation

Section 6.8.1 shall be conducted for both safety analysis set and non-safety analysis set. Section 6.8.2, 6.8.3 and 6.8.5 will be performed on the safety analysis dataset and section 6.8.4 will be performed on the non-safety analysis set.

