6.8.1 Summary of Adverse Events

The summary table of adverse events will be presented about the following items. The number of

subjects, incidence proportion, its 95% confidence interval and the number of adverse events will be presented in the summary table. The analysis of adverse event/serious adverse event during the 30-day (Day 1 to Day 30) after each vaccine dose will be also performed separately.

- Adverse event (AE) · Adverse drug reaction (ADR) ^a
- Serious adverse event · Serious adverse drug reaction
- Unexpected adverse event ^b · Unexpected adverse drug reaction
- Unexpected serious adverse event · Unexpected serious adverse drug reaction
- Unexpected non-serious adverse event ^c · Unexpected non-serious adverse drug reaction

^a Adverse drug reaction (ADR): Adverse event that the 'relate to Cervarix' is 'Certain', 'Probable / Likely', 'Possible', 'Conditional / Unclassified' and 'Unassessable / Unclassifiable'

^b Unexpected adverse event: Adverse event that is not included in the local product insert

^c Unexpected non-serious adverse event: Adverse event that is non-serious and not included in the local product insert

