6.8.2 Adverse Events by Preferred Term

All adverse events that occurred after the vaccination of Cervarix will be classified by terminology of System Organ Classes (SOC) and Preferred Term (PT) or Included Term (IT) of World Health Organization–Adverse Reaction Terminology (WHO-ART).

About the following items, adverse events of the subjects which occurred during or after the vaccination of Cervarix in accordance with SOC, PT or IT will be presented for the number of subjects, incidence proportion and its 95% confidence interval using exact method and the number of adverse events. At the time, even if one subject has 2 or more adverse events in one category, it will be analyzed as one within the category. Also, one subject may be presented as a duplicate in different categories.

- Adverse event · Adverse drug reaction
- Serious adverse event · Serious adverse drug reaction
- Unexpected adverse events · Unexpected adverse drug reaction
- Unexpected serious adverse events · Unexpected serious adverse drug reaction
- Unexpected non-serious adverse events · Unexpected non-serious adverse drug reaction

For all adverse events, the number of adverse events will be presented by following items. Additionally, all adverse events will be classified by System Organ Classes (SOC) and Preferred Term

(PT) or Included Term (IT) and presented as the number of each adverse events.

- Site
- Outcome
- Maximum intensity
- Relate to Cervarix
- Medically attended visit

Detailed adverse events will be listed by subjects for the following items.

- Serious adverse event
- Unexpected adverse event
- Unexpected serious adverse event
- Adverse event of subject with liver disease
- Adverse event of subject with renal disease
- Adverse event leading to withdrawal ^a

^a Adverse event leading to withdrawal: In case that 'Did the subject return for the visit?' is 'No' and major reason is 'Serious Adverse Event and/or Non-Serious related AE' in at least one visit

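### The SAP's listing of adverse events leading to withdrawal admits non-serious events only if related, whereas the protocol sets no causality limit

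*SAP*

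**What the plan says.** Protocol 10.2 sets the principle: "Subjects who are withdrawn because of SAEs/AEs must be clearly distinguished from subjects who are withdrawn for other reasons". Protocol 10.2.1 then gives the reasons that the physician may record. A serious adverse event, a "Non-serious adverse event" and death are three separate entries, and none carries a causality qualifier. The same section defines a withdrawal as "any subject who did not come back for the concluding visit/was not available for the concluding contact foreseen in the protocol". For the analysis, protocol 11.5.2.1 says that "Serious adverse events and withdrawals due to adverse events reported during the PMS period" will be described in detail.

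The SAP implements this as one of six by-subject listings in 6.8.2. Its footnote a sets two conditions. The first is non-return: "In case that 'Did the subject return for the visit?' is 'No". The second is the reason: "major reason is 'Serious Adverse Event and/or Non-Serious related AE' in at least one visit". SAP 6.8.4 asks for the same listing in the non-safety set and gives no definition of its own. SAP 6.8 assigns the populations: "Section 6.8.2, 6.8.3 and 6.8.5 will be performed on the safety analysis dataset", with 6.8.4 run on the non-safety set.

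**The concern.** The footnote adds the word related, which the protocol does not use here. A withdrawal listing exists to show which events subjects or physicians found reason enough to stop. Filtering it on the physician's causality opinion removes some of those cases before anyone reviews them. Safety is the only objective of this surveillance, and this is an output that the protocol specifically promises.

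SAP section 1 presents the document as based on the protocol's statistical methods, and nothing in it flags or explains the narrowing. Protocol 11.4 requires changes from the planned analysis to be described and justified in the final report. As things stand, a reader of that report could take the listing as complete when it is not.

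**Working it through.** No sample size, rate or test is involved, so the check is a comparison of texts.

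**Step 1: what related means.** The footnote does not define it. The nearest rule is the ADR definition in SAP 6.8.1, which counts events rated '"Certain', 'Probable / Likely', 'Possible', 'Conditional / Unclassified' and 'Unassessable / Unclassifiable"' as reactions. That is five of the six causality levels in SAP 7.2, and the one left out is Unlikely. On this reading the footnote loses only events rated Unlikely. A narrower reading of related would lose more.

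**Step 2: each withdrawal reason under the two documents,** given that the non-return condition is met.

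| Reason for withdrawal | AE withdrawal under protocol 10.2.1 | In the SAP withdrawal listing | In another by-subject listing of SAP 6.8.2 |
|---|---|---|---|
| Serious AE | Yes | Yes | Yes, serious AE |
| Non-serious AE, any of the five ADR levels | Yes | Yes, if related means ADR | Only if unexpected, or liver or renal disease |
| Non-serious AE, Unlikely, unexpected | Yes | No | Yes, unexpected AE |
| Non-serious AE, Unlikely, expected, liver or renal disease | Yes | No | Yes, liver or renal disease |
| Non-serious AE, Unlikely, expected, no liver or renal disease | Yes | No | None |
| Death | Separate reason | No | Yes, serious AE |

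**Step 3: what is lost.** Rows three to five are adverse event withdrawals under the protocol that the SAP listing does not show. In rows three and four the event is listed by subject, but under a heading that does not identify it as a cause of withdrawal. In row five it is not listed individually at all. In all three rows, for subjects in the safety set, the event still enters the summary table (6.8.1) and the tables by term, intensity and causality (6.8.2).

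**Step 4: is there a broader output elsewhere?** The disposition table in SAP 6.1 covers enrolment, vaccination and analysis-set membership, not withdrawal reasons. No other SAP section describes adverse event withdrawals. The mock-up tables and the CRF are not available, so this rests on the SAP text.

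**The case against.** The strongest reply is that both footnote conditions stand in quotation marks and look like CRF field labels. If so, the SAP is only mapping the data collected. That is plausible but cannot be confirmed. It would move the mismatch with protocol 10.2.1 to data capture without removing it, and a footnote could not then recover reasons that were never recorded.

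The second reply is that little is lost: probably only events rated Unlikely, all still counted in the aggregate tables and some listed elsewhere. This stands, and it limits the point to one descriptive listing.

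Three stronger readings are tempting, and the documents do not support them:

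- **Deaths vanish because the footnote omits death.** Protocol 8.1.3 makes any event resulting in death serious, so it is listed by subject as a serious adverse event for anyone in the analysis sets. Protocol 10.2.1 itself keeps death apart from the two adverse event reasons.
- **Nothing can trigger the listing after the last dose, because Visits 1 to 3 are all dosing visits.** The protocol foresees follow-up after the last dose, a CRF conclusion 30 days after it (Table 3, note b), and a concluding visit or contact. Whether the CRF asks the return question there is unknown. The non-return condition broadly tracks the protocol's own definition of withdrawal.
- **The dropout allowance gives a count.** Protocol 11.2 and SAP 2.2 imply 660 − 600 = 60 subjects, but from all causes. Any share assigned to adverse events would be invented, and it would count all such withdrawals, not those missed. Many of the 60 might also enter neither analysis set: SAP 4.1 requires completed 30-day follow-up after at least one dose, and SAP 4.2 leaves out follow-up failures.

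**Conclusion.** The point holds on the causality restriction alone. A withdrawal for a non-serious adverse event judged unrelated must be distinguished and described under protocol 10.2, 10.2.1 and 11.5.2.1, but SAP 6.8.2 leaves it out of the withdrawal listing, and 6.8.4 inherits the omission. That related excludes only Unlikely is an assumption, since the footnote does not say so. The number of subjects affected cannot be estimated from the documents. The consequence is an incomplete listing and an unstated departure from the protocol. No incidence proportion or confidence interval changes, so this is worth correcting but minor.

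**What to change.** Reword footnote a in SAP 6.8.2, and have 6.8.4 refer to it: an adverse event leads to withdrawal when the recorded reason is a serious adverse event, or a non-serious adverse event of any causality, at any visit or at the concluding visit or contact (the PMS conclusion page). Show causality as a column in the listing. The cost is one footnote and one column.

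Check the CRF at the same time. If its option says related, align the label with protocol 10.2.1. If that is no longer practical, keep the narrower definition, state it openly in the SAP, and describe and justify it in the final report as protocol 11.4 requires. This change leaves the analysis sets as they are, so it will not bring in subjects who belong to neither set.

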6.8.3 Incidence Proportion by Baseline Background Factor

For all adverse events, the number of subjects to whom adverse event occurred and the number of adverse events will be presented per each categorical baseline background factor and special study group described in section 6.2 ~ 6.7. Also, the incidence proportion of adverse event and its 95% confidence interval will be presented.

The incidence proportion of adverse event and its 95% confidence interval will be presented and analyzed using Chi-square test or Fisher's exact test per each baseline background factor. However, some continuous variables not categorized such as height, weight will be excluded from analysis.

In the re-examination, multiple logistic regression will be performed to identify the factors that affect the incidence proportion by baseline background factor and special study group. All of factors that are statistically significant (p-value < 0.05) will be included in the model. However, as considering the structure and characteristics of the collected data, the factors used for the actual analysis can be added or subtracted.

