## 7.4. Concomitant medication/vaccination (Amended: 14 May 2018)

All concomitant vaccinations according to local practice are allowed during the PMS. *Collected information for concomitant medication/vaccination such as trade/generic name, route, frequency, total daily dose (dose, unit), start date, end date, indication etc. needs to be recorded in the CRF.* The medication/vaccination history (within 30-days prior to the *Cervarix* vaccination) should be documented in the CRF. For subjects who have received any of their dose/s of *Cervarix* outside the PMS and appear for the subsequent dose/s in this PMS, previous *Cervarix* vaccination history will be reported starting at first visit onwards irrespective of the dose subject has appeared for in the PMS. (Refer to the [Table 1](#)).

At each PMS visit/contact, the physician should question the subjects or subject's parent(s)/LAR(s) about any medication taken and vaccination received by the subject.

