### 7.4.1. Recording of concomitant medications/products and concomitant vaccination

The following concomitant medications/products/vaccines must be recorded in the eCRF/CRF or the **SAE/ADR** Report if administered during the indicated recording period:

- All concomitant medication/vaccination, with the exception of vitamins and/or dietary supplements, are to be recorded in the CRF. This also applies to concomitant medication administered prophylactically in anticipation of reaction to the vaccination and any medication intended to treat an AE.
- A prophylactic medication is a medication administered in the absence of ANY symptom and in anticipation of a reaction to the vaccination (e.g. an anti-pyretic is considered to be prophylactic when it is given in the absence of fever and any other symptom, to prevent fever from occurring [fever is defined as temperature  $\geq 37.5^{\circ}\text{C}$  ( $99.5^{\circ}\text{F}$ ) on oral/axillary/ tympanic setting, or  $\geq 38.0^{\circ}\text{C}$  ( $100.4^{\circ}\text{F}$ ) on rectal setting]).
- Similarly, concomitant medication administered for the treatment of an SAE, at any time, must be recorded on the CRF concomitant medication section and in the PMS SAE report form, as applicable. Refer to Section [8.1.3](#) for the definition of a SAE.

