### **8.6. Treatment of AEs**

Treatment of any adverse event is at the sole discretion of the physician and according to current good medical practice. Any medication administered for the treatment of an AE should be recorded in the subject's CRF.

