6.5 Medication

The following categorical data will be summarized with descriptive statistics. The concomitant medication during the 30-day (Day 1 to Day 30) after each vaccine dose will be also tabulated using descriptive statistics.

- Prior medication ^a
- Concomitant medication ^b

^a Prior medication: In case of that has/have been administered medication(s)/treatment(s) within 30 days (day -29 to day 1) prior Cervarix vaccination

^b Concomitant medication: In case of that has/have been administered medication(s)/treatment(s) within 30 days (day 1 to day 30) after Cervarix vaccination

In re-examination report, the prior / concomitant medication could be classified by main category and sub category of Korea Index of Medical Specialties (KIMS).

If one subjects has two or more medication in one category, it will be analyzed as one subject within the category. Also, the one subject may appear as a duplicate in different categories.

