6.6 Vaccination

The following categorical data will be summarized with descriptive statistics. The concomitant vaccination during the 30-day (Day 1 to Day 30) after each vaccine dose will be also tabulated using descriptive statistics.

- Prior vaccination ^a
- Concomitant vaccination ^b

^a Prior vaccination: In case of that has/have been administered any vaccine(s) other than Cervarix within 30 days (day -29 to day 1) prior Cervarix vaccination

^b Concomitant vaccination: In case of that has/have been administered any vaccine(s) other than Cervarix within 30 days (day 1 to day 30) after Cervarix vaccination

In re-examination report, the prior / concomitant vaccination could be classified by main category and sub category of Korea Index of Medical Specialties (KIMS).

If one subjects has two or more vaccination in one category, it will be analyzed as one subject within the category. Also, the one subject may appear as a duplicate in different categories.

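### SAP 6.8.3 tests AE incidence against post-vaccination factors as if they were baseline, chiefly concomitant medication (which includes AE treatment) and in-PMS dose count (which sets observation time)

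*SAP*

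**What the plan says.** SAP 6.8.3 states that AE counts "will be presented per each categorical baseline background factor and special study group described in section 6.2 ~ 6.7". Incidence is then compared by chi-square or by Fisher's "exact test per each baseline background factor". At re-examination a multiple logistic regression is to identify factors that affect incidence: "All of factors that are statistically significant (p-value < 0.05) will be included in the model". SAP 5.5 skips the model if two or fewer factors are significant. A closing clause in 6.8.3 lets factors be added or dropped in view of the data.

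Sections 6.2 to 6.7 include four items that are not, or need not be, fixed at baseline:

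- **Concomitant medication (SAP 6.5):** "Concomitant medication: In case of that has/have been administered medication(s)/treatment(s) within 30 days (day 1 to day 30) after Cervarix vaccination". Protocol 7.4.1 requires all concomitant medication except vitamins and dietary supplements to be recorded, and adds: "This also applies to concomitant medication administered prophylactically in anticipation of reaction to the vaccination and any medication intended to treat an AE". Protocol 8.6 repeats it: "Any medication administered for the treatment of an AE should be recorded" in the CRF.
- **Concomitant vaccination (SAP 6.6):** "any vaccine(s) other than Cervarix within 30 days (day 1 to day 30) after Cervarix vaccination".
- **Total number of Cervarix vaccinations in the PMS (SAP 6.7):** one, two or three doses (SAP 7.2). Protocol 3 follows AEs for 30 days after each in-PMS dose and allows entry at any dose. Protocol 10.1 counts a subject as complete after one followed dose.
- **Pregnancy (SAP 6.2):** the Protocol synopsis follows subjects who become pregnant within 30 days after a dose.

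SAP 5.5 names concomitant medication and concomitant vaccination inside its denominator rule for AE incidence by baseline background factor. The only factors 6.8.3 excludes by name are uncategorised continuous ones such as height and weight.

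**The concern.** A comparison by a baseline factor can be read as a difference in risk only if the outcome cannot influence the factor and the groups are observed for the same time. Concomitant medication fails the first condition: a subject whose AE is treated with a recorded drug moves into the Yes group because of the AE. Dose count fails the second, since a three-dose subject has three 30-day windows in which to report an AE. It can also fail the first, because an AE may end the series. Concomitant vaccination and medication share the window problem, as their recording period also lengthens with each dose.

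The resulting p-values would be reported as findings on baseline factors. They would also count towards the three significant factors that trigger the re-examination model, and could enter it.

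**Working it through.** **Figures in the plan.** Neither document gives an error rate or power for the 6.8.3 tests. The precision figures they do give are sound. Exact (Clopper-Pearson) limits at n=600 reproduce all eight rows of Protocol Table 6 (for example 60/600: 7.7% to 12.7%), and 600 × 1.10 = 660. The inputs taken from the documents are N = 600, two-sided 0.05, and the SAP 5.5 rule of Fisher when more than 20% of expected cells are below 5. All rates below are assumptions, shown as ranges.

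**1. Concomitant medication.** Let *b* be drug use unrelated to AEs, *t* the share of AEs treated with a recorded drug, and *p* the AE prevalence. The drug has no effect on AE risk.

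- P(med | AE) = 1 − (1 − b)(1 − t); P(med | no AE) = b
- OR = [1 − (1 − b)(1 − t)] / [b(1 − t)]

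Middle case, p = 0.10, b = 0.20, t = 0.20:

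- P(med | AE) = 1 − 0.8 × 0.8 = 0.36
- AE incidence, users: 0.036 / (0.036 + 0.180) = 16.7%
- AE incidence, non-users: 0.064 / (0.064 + 0.720) = 8.2%
- OR = 0.36 / 0.16 = 2.25; p<0.05 in 78% of simulated surveillances

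Over p = 2, 5, 10, 20% and b = 10, 20, 30% (4000 runs per cell):

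| AEs treated | OR | p<0.05 (nominal 5%) |
|---|---|---|
| 10% | 1.4–2.1 | 8–75% |
| 20% | 1.8–3.5 | 17–100% |
| 40% | 3.2–7.7 | 50–100% |

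With 20% or more treated, 19 of 24 cells exceed 50%. In a separate chi-square run with no AE treated, rejection was 4.2–5.3%, so the excess comes from AE treatment.

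**2. Dose count.** With a constant, independent risk *r* per dose, incidence after *k* doses is 1 − (1 − r)^k. At r = 5% this is 5.0%, 9.8% and 14.3% for one, two and three doses, although the risk per dose is identical. The table gives the percentage of runs with p<0.05 at r = 2 / 5 / 10%:

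| Planned 1/2/3 doses | Stop after an AE | AEs independent across doses | Within-subject correlation 0.5 |
|---|---|---|---|
| 150/250/200 | none | 33 / 74 / 97 | 9 / 20 / 40 |
| 20/80/500 | none | 4 / 16 / 48 | 1 / 3 / 6 |
| 150/250/200 | 20% | 11 / 26 / 48 | 5 / 6 / 5 |
| 20/80/500 | 20% | 27 / 42 / 54 | 54 / 80 / 97 |

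The reversal can be followed by hand (20/80/500, r = 5%, independent, 20% stop, so 5% × 20% = 1% leave after each dose):

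- One dose received: 20 + 580 × 0.01 = 25.8 subjects; with an AE 1 + 5.8 = 6.8, or 26.4%
- Two doses: 80 × 0.99 + 500 × 0.99 × 0.01 = 84.15; with an AE 80 × (0.05 × 0.8 + 0.95 × 0.05) + 4.95 = 11.95, or 14.2%
- Three doses: 500 × 0.99² = 490.05; with an AE 490.05 − 500 × 0.95³ = 61.36, or 12.5%

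Fewer doses now appear to carry more risk. In a separate run without stopping, comparing the groups on one common 30-day window gave 4.3–5.3%.

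**3. Concomitant vaccination, or medication with AE drugs excluded.** Only the unequal windows remain: OR 1.01–1.33, rejection 4–23%, and at most 9% with correlation 0.3–0.5.

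**4. Check of the remedy.** Prior medication taken before the first in-PMS dose rejects in 1.6–7.0%. If 'prior' is read as before each dose, the 30 days before a second dose given at 1 month are the follow-up of dose 1. AE treatment then re-enters: OR 1.1–2.5, rejection 7–94%.

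**The case against.** The PMS is descriptive, its interim results do not alter conduct (Protocol 11.4.2), and a per-dose AE summary is already planned (SAP 6.8.1). The model may be skipped, and factors may be dropped from it. This limits the consequence but does not remove the fault: the add-or-drop clause is discretionary, used after the data are seen, and leaves the univariate tests in place.

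No passage calls in-PMS dose count a baseline factor by name. It comes in through the sweep of 6.2 to 6.7 and its categories in 7.2. One could read that sweep as covering only truly baseline items, but SAP 5.5 applies the label to concomitant medication, so the SAP does not draw that line. The dose-count figures vary widely with unknown inputs, and the reversed example rests on about 26 one-dose subjects. It shows what can happen, not what is likely. The 30, 60 and 90 days apply to AE windows; SAEs are followed continuously to 30 days after the last dose.

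The sentence planning chi-square or Fisher tests names background factors only, so pregnancy, a special group, may be merely tabulated at that step. The model sentence does name special groups, so it can be reached there. No size was computed for pregnancy.

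At an AE rate of 2% the medication bias is often modest, and about 24% of runs have fewer than 10 AE subjects, where SAP 5.5 allows a listing instead. Protocol Table 3 marks medication history at Visit 1 only, which favours the single-window reading of 'prior'; SAP 6.5 leaves it open.

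**Conclusion.** The concern holds. As written, SAP 6.8.3 produces associations that do not reflect differences in risk. For concomitant medication the direction is certain whenever any AE is treated with a recorded drug. The size depends on assumed rates: 8–75% false significance with 10% of AEs treated, and usually above 50% with 20% or more. The dose-count test cannot be interpreted in either direction, because its error depends on dose mix, within-subject correlation and stopping after an AE, none of which the documents give. The bias for concomitant vaccination is small. The overall, per-dose and preferred-term AE proportions and their exact intervals are untouched. This should be corrected before the re-examination analysis, but it does not threaten the main safety estimates.

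**What to change.** In SAP 6.8.3, limit the chi-square and Fisher tests and the logistic model to factors fixed before the first in-PMS dose. Prior medication and prior vaccination stay as tested factors, with 6.5 and 6.6 stating that 'prior' means the 30 days before the first in-PMS injection. Tabulate AE incidence by concomitant medication, concomitant vaccination, total in-PMS doses and pregnancy (kept as a special group) descriptively, without p-values or model entry.

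If the sponsor wants a tested concomitant-medication factor, the narrower option is to exclude drugs whose recorded indication is an AE. Protocol 7.4 already collects this: "total daily dose (dose, unit), start date, end date, indication etc. needs to be recorded in the CRF". That removes most of the bias but leaves the unequal-window part (rejection 4–23%).

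The cost is SAP wording only. No new data are needed and the special-group tables remain. The one loss is that post-vaccination factors are shown but no longer tested.
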